11 STATISTICAL AND ANALYSIS ISSUES

11.1 Adjustments for Covariates

The baseline blood bicarbonate and baseline eGFR, as continuous covariates, will be included in an MMRM model for analysis of change from baseline in blood bicarbonate. Other baseline values of continuous efficacy variables will be included in MMRM models (see Section 14.4.2) or analysis of covariance (ANCOVA) models (see Section 14.7) as covariates.

Two stratification variables, Baseline blood bicarbonate (≤ 18 versus > 18 mEq/L) and Screening eGFR (< 30 versus ≥ 30 mL/min/1.73m²), are utilized in the randomization. They will be used as subgroups (see Section 11.10) to evaluate primary and secondary efficacy variables. Other baseline characteristics, such as age, sex, race, baseline alkali therapy, and geographic region, may also be used as subgroups (see Section 11.10).

11.2 Handling Dropouts or Missing Data

Missing data will not be imputed, unless otherwise specified. Early termination visits will be mapped to the next scheduled visit for inclusion in summary tables, where appropriate. For example, subjects who terminate after Week 11 (e.g., have assessments through Week 11) would have their early termination assessments mapped to the next scheduled visit (i.e. Week 12) based on the analysis window (See Section 10.2).

Every effort will be made to ensure completeness of data collection. If severity or relationship of an AE to study drug is not recorded, the severity or relationship will be imputed as “severe” or relationship as “possibly related”, for analysis purposes. In the subject listing, both collected and imputed values will be presented.

11.3 Handling of Efficacy Data

The primary analysis will not impute missing (blood bicarbonate) data. For the primary analysis, missing data in both placebo and TRC101 will be assumed to be missing at random (MAR). Subject withdrawal patterns in the placebo and TRC101 groups will be assessed. Sensitivity analyses for the primary and secondary efficacy endpoints (Section 14.5) will use multiple imputation models assuming the data are missing not at random (MNAR).

11.4 Handling of Safety Data

11.4.1 Adverse Events

All AE verbatim terms reported on the eCRFs will be coded using the Medical Dictionary for Regulatory Activities (MedDRA® version 20.0). TEAEs are defined as any AEs, regardless of relationship to study drug, that have an onset or worsening in severity on or after the first dose of study drug. If it cannot be determined whether the AE is treatment-emergent because of a partial onset date, the event will be counted as a TEAE. Adverse events with incomplete start dates will be considered TEAEs, if:

- Onset time is missing but the onset date is on Day 0 or Study Day 1.
- Day and month are missing and the year is equal to or after the year of the first date of study drug dosing;
- Day is missing and the year is after the year of the first date of study drug dosing;
- Day is missing and the year is equal to the year of the first date of study drug dosing and the month is equal to or after the month of the first date of study drug dosing; or
- Year is missing.

Related AEs are those with relationship to study drug reported as “possible”, “probable” or “related”.

11.4.2 Concomitant Medications

All medication verbatim terms reported on the eCRFs will be mapped according to the World Health Organization (WHO) Drug Dictionary (WHO DD Enhanced version, March 1st, 2017, B2 format). The medications will be mapped to Anatomical/Therapeutic/Chemical (ATC) class and preferred names. A prior medication is considered to be any medication that is taken prior to the first study drug dosing. A concomitant medication is considered to be any medication taken after the start of study drug dosing. Specifically, concomitant medications are medications:

- that are continued from Screening and continued after the first study drug dosing,
- with start dates or stop dates within the Treatment Period

If start date is missing, the medication will be considered to have started prior to the study. Such a medication may also be considered concomitant, depending on the stop date or lack thereof. If the stop date of a concomitant medication is missing, then the medication will be treated as ongoing. If the start date of a medication is missing, the stop date will be used to determine whether

or not it is concomitant. Medications with other incomplete start dates will be identified as concomitant using the same algorithm as above for TEAEs, if the stop date information is insufficient for the determination.

During the study, alkali dose will be monitored; the protocol specifies that the dose of oral alkali, if any, should not change during the study. Any change in equivalent dose during the study when the type of alkali has changed (e.g. sodium citrate to sodium bicarbonate) will be identified.

11.5 Interim Analyses and Data Monitoring

There will be no interim analyses of efficacy. Safety data monitoring is described in Section 15.9.

11.6 Multicenter Considerations

Thirty-seven (37) study centers in Europe and the United States randomized at least 1 subject in the study as follows: European Union (EU) countries (8 sites with 82 subjects); Non-EU countries (17 sites with 108 subjects); and the United States (12 sites with 27 subjects). Data from all study centers will be pooled for efficacy and safety analyses as well as for summaries. Because the number of subjects at each center is likely to be small, no analyses will be performed by center. Geographic region (i.e., EU, Non-EU, and US), in which study sites in certain geographic locations will be pooled together, will be used for subgroup analyses. The table below lists these study centers with their site identification number, country and geographic region category.

Table 3 Country Code and Geographic Region Category

Site Identification Number	Country Code	Country Name	Geographic Region
11	BGR	Bulgaria	EU
21	HRV	Croatia	EU
41	HUN	Hungary	EU
44	HUN	Hungary	EU
46	HUN	Hungary	EU
49	HUN	Hungary	EU
71	SVN	Slovenia	EU
72	SVN	Slovenia	EU
31	GEO	Georgia	Non-EU
32	GEO	Georgia	Non-EU
33	GEO	Georgia	Non-EU

Table 3 Country Code and Geographic Region Category

Site Identification Number	Country Code	Country Name	Geographic Region
34	GEO	Georgia	Non-EU
35	GEO	Georgia	Non-EU
36	GEO	Georgia	Non-EU
37	GEO	Georgia	Non-EU
61	SRB	Serbia	Non-EU
64	SRB	Serbia	Non-EU
65	SRB	Serbia	Non-EU
81	UKR	Ukraine	Non-EU
83	UKR	Ukraine	Non-EU
84	UKR	Ukraine	Non-EU
85	UKR	Ukraine	Non-EU
86	UKR	Ukraine	Non-EU
87	UKR	Ukraine	Non-EU
88	UKR	Ukraine	Non-EU
52	USA	United States	USA
53	USA	United States	USA
54	USA	United States	USA
55	USA	United States	USA
56	USA	United States	USA
57	USA	United States	USA
58	USA	United States	USA
59	USA	United States	USA
91	USA	United States	USA
92	USA	United States	USA
93	USA	United States	USA
95	USA	United States	USA

11.7 Multiple Comparisons, Multiplicity

In order to control family-wise error rate, formal statistical testing for the primary and secondary endpoints will be performed sequentially. At the Week 12 Visit, a formal comparison between the TRC101 and the placebo groups will be performed using Fisher's exact test for the proportion of subjects having a CFB in blood bicarbonate ≥ 4 mEq/L or having blood bicarbonate in the normal range. Only when this comparison is statistically significant at the two-sided 0.05 level, will a

formal test for the secondary efficacy endpoint (CFB in blood bicarbonate at the Week 12 Visit) be performed. A MMRM model will be used to compare the group least squares (LS) means of change in blood bicarbonate at Week 12.

11.8 Use of an “Efficacy Subset” of Subjects

All efficacy analyses will be performed using the MITT analysis set, based on the assigned treatment group. In addition, the primary and secondary efficacy analyses will use the PP analysis set as a supportive evaluation of efficacy of TRC101.

11.9 Active-Control Studies

The placebo group will serve as a comparator in this study.

11.10 Examination of Subgroups

Subjects will be categorized into the following subgroups for the purposes of exploring primary and secondary efficacy endpoints. These subgroups may also be used for safety evaluations. Forest plots will be generated to display the primary and secondary results from the above subgroups, along with the overall results.

- Baseline blood bicarbonate (≤ 18 versus > 18 mEq/L)
- Screening eGFR (< 30 versus ≥ 30 mL/min/1.73m²)
- Age (< 65 versus ≥ 65 years)
- Sex (Male versus Female)
- Race (White versus Non-White)
- Baseline alkali use (Yes versus No)
- Geographic region (EU, Non-EU, US)
- Dose titration status during the study (no titration, any up-titration, any down-titration)

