5.3 Dosing Regimen

The study drug dose titration algorithm is described in [Appendix 2](#). Dose titrations can only be performed during a clinic visit. If the dose of study drug is changed, the subject will start the new dose at lunch time on the titration day. Dose titrations should be performed on the basis of onsite i-STAT blood bicarbonate measurements only.

The study drug dose will be fixed for the first 4 weeks of the Treatment Period (during this time each subject will receive the study drug dose assigned at randomization [Baseline Visit]); no study drug dose adjustments will be permitted before the Week 4 Visit, except for subjects with elevation of blood bicarbonate ≥ 27 mEq/L. If the blood bicarbonate level is 27 to 30 mEq/L at any time during the Treatment Period through Week 11, the study drug dose will be decreased by 1 packet/day (minimum dose is 0 packets/day). Beginning at the Week 4 Visit, subjects with a blood bicarbonate level below the normal range (< 22 mEq/L) will have a blinded adjustment of the study drug dose in accordance with the titration algorithm (see [Appendix 2](#)). The study drug dose will only be titrated if NO dose changes have been made during the previous 14 days. If blood bicarbonate is confirmed to be > 30 mEq/L at any time during the study, the study drug treatment will be interrupted, no study drug will be dispensed to the subject, and the subject will be invited for a visit in approximately 1 week to retest blood bicarbonate. If blood bicarbonate decreases to < 27 mEq/L and the subject is still within the Treatment Period, study drug should be re-started at a lower dose in accordance with the titration algorithm (see [Appendix 2](#)). If blood bicarbonate is ≥ 27 mEq/L, the study drug dosing should be withheld until blood bicarbonate is < 27 mEq/L.

No dose titration will be allowed after Week 11 (i.e., 77 days after the day of the first dose). Dose titrations are blinded.

The Medical Monitor must be notified within 24 hours of confirmation of a bicarbonate value > 30 mEq/L or < 12 mEq/L. Dose interruptions due to blood bicarbonate elevations should be performed on the basis of i-STAT measurements, except in unusual situations when they may be based on confirmed non-i-STAT blood bicarbonate values > 30 mEq/L, e.g., if i-STAT values cannot be obtained because the subject is hospitalized.

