7.3.1 Efficacy Measurements

Fasting blood bicarbonate levels measured onsite with an i-STAT point-of-care device will be used to determine the primary and secondary efficacy endpoints for this study. Exploratory efficacy measurements include: repeated chair stand test, and kidney disease quality of life questionnaire (KDQOL) Question 3. Other efficacy measurements include blood and urine biomarkers related to bone and kidney health.

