14.3.1 Reporting Results

The number and proportions (expressed as percentages) of subjects who are responders at each time point and at the end of treatment will be calculated. A responder is defined as a subject who has a change from baseline in blood bicarbonate ≥ 4 mEq/L or has a blood bicarbonate in the normal range (22 to 29 mEq/L). The difference in proportion of responders between TRC101 and placebo subjects and its two-sided exact (Clopper Pearson) 95% CI, as well as the p-value from Fisher's exact test comparing the TRC101 group and the placebo group, will be reported by time point. The exact 95% CIs will also be presented by treatment group and time point.

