14.4 Secondary Efficacy Analysis

The secondary analysis will be performed on the MITT analysis set, with the PP analysis set as supportive. All scheduled blood bicarbonate values collected through the Week 12 visit will contribute to the analysis. The efficacy variable, the change from baseline in blood bicarbonate value, will be calculated for each time point after the first dose through the Week 12 visit (i.e., Weeks 1, 2, ..., 12). Missing data will not be imputed for the main analysis but will be imputed for the sensitivity analysis (Section 14.5). The analysis will test the difference in LS means between TRC101 and placebo at Week 12.

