14.6 Subgroup Analyses of the Primary and Secondary Efficacy Endpoints

Subgroups defined in Section 11.10 will be used to explore the effect of the primary and secondary efficacy endpoints by intrinsic and extrinsic factors. The subgroup analyses for the primary efficacy endpoint will be analyzed as described in Section 14.3.1. The subgroup analyses for the secondary efficacy endpoint will be analyzed as described in Sections 14.4.2 and 14.4.3.

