14.8.4 Subgroup Analysis of Change in i-STAT Blood Bicarbonate Over Time

The treatment effect on i-STAT blood bicarbonate in subjects from different randomization strata (i.e., baseline blood bicarbonate \leq 18 versus $>$ 18 mEq/L and screening eGFR $<$ 30 versus \geq 30 mL/min/1.73m²) and dose titration status (i.e., receiving only 2 packets throughout entire study, up-titrated to 3 packets at any time, and down-titrated to 1 or 0 packet at any time) will be evaluated. The blood bicarbonate values, as measured by an i-STAT point-of-care device, along with change from baseline values, will be summarized by treatment and time point for each stratum and each titration status.

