16 CHANGES RELATIVE TO THE PROTOCOL-SPECIFIED ANALYSIS

16.1 Other Efficacy Analyses

SAP Section 14.8 contains additional efficacy and dosing analyses that were not described in the protocol as follows:

- Additional categorical thresholds of bicarbonate increase (≥ 2 mEq/L and ≥ 3 mEq/L) was added to further understand potential treatment effect on bicarbonate increase in lower ranges.
- Baseline descriptor of kidney failure risk at 2 and 5 years (i.e., Kidney Failure Risk Equation score) was added to describe baseline kidney failure risks in the study population.

- Analyses exploring the effects of starting dose and dose titration.

While the protocol specified one of the safety endpoints as “Having met the high bicarbonate dose interruption criterion (confirmed > 30 mEq/L) at any time during the Treatment Period.”, SAP Section 15.3 describes summaries of subjects who had a bicarbonate > 30 mEq/L event. Removing the “confirmed” qualifier should capture any subjects potentially meeting the high bicarbonate dose interruption criterion at any time during the Treatment Period.

17 Reference

1. Yuan Y. Sensitivity Analysis in Multiple Imputation for Missing Data, SAS Institute Inc. <http://support.sas.com/resources/papers/proceedings14/SAS270-2014.pdf>
2. Tangri, et al. A predictive model for progression of chronic kidney disease to kidney failure JAMA. 2011;305(15):1553-1559
3. Hays RD, et al. Kidney Disease Quality of Life Short Form (KDQOL-SFtm), Version 1.3: A Manual for Use and Scoring. Rand, 1997.

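### Dose-titration status is a post-randomisation outcome, yet the SAP analyses it as a between-arm efficacy subgroup, and two of its three rows are expected to hold almost no placebo subjects

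*SAP*

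**What the plan says.** - SAP 11.10 names eight factors for exploring the primary and secondary endpoints, with forest plots. Seven are baseline characteristics. The eighth is "Dose titration status during the study (no titration, any up-titration, any down-titration").
- SAP 14.6 makes no exception for it: "The subgroup analyses for the primary efficacy endpoint will be analyzed as described in Section 14.3.1", which means a TRC101 minus placebo difference with a Fisher p-value. The secondary endpoint follows 14.4.2 and 14.4.3, an MMRM difference in LS means.
- SAP 14.3.1 also shows response within each arm: "The exact 95% CIs will also be presented by treatment group and time point".
- Protocol 5.3 on what drives titration: "Dose titrations should be performed on the basis of onsite i-STAT blood bicarbonate measurements only". Under Appendix 2, a value of 27 to 30 mEq/L triggers a decrease at any point through Week 11, and 12 to <22 triggers an increase from Week 4. Protocol 5.7 applies this blinded in both arms.
- SAP 7.3.1 on the endpoints: fasting bicarbonate "measured onsite with an i-STAT point-of-care device will be used to determine the primary and secondary efficacy endpoints".
- SAP 14.8.4 separately summarises bicarbonate by arm and titration status, but by packet level: only 2 packets throughout, raised to 3, or "down-titrated to 1 or 0 packet at any time".
- SAP 16.1 describes the added work in 14.8 as "Analyses exploring the effects of starting dose and dose titration", without a caveat.

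**The concern.** A subgroup factor should be fixed before treatment can influence it. Titration status is instead a coarse summary of the response itself. Among completers, the no-titration row is mostly subjects who sat at 22 to <27 mEq/L from Week 4 on. On TRC101 that is a good response to drug; on placebo it is a rare fluctuation. The two are not comparable, whatever the sample size.

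Three practical problems follow.

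- Two rows may have too few placebo subjects for any comparison.
- TRC101 response rates will differ between rows even if titration does nothing, and the wording in SAP 16.1 invites reading such a contrast as an effect.
- The any-up and any-down rows overlap, and 11.10 and 14.8.4 class some subjects differently. A 2-3-2 packet course is any-down in 11.10 but never reaches 1 or 0 packets; a 2-1-2 course is any-up but never reaches 3.

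**Working it through.** **Inputs.** From SAP 8.2: mean changes at Weeks 1, 2, 4, 6, 8, 10, 12 (placebo 0.85 falling to 0.25; TRC101 2.00 rising to 4.25), SD 3.0, and the correlation matrix (0.6 at adjacent visits, 0.078 at the longest lag). Arms of 90 and 120. Rules from Protocol Appendix 2. SAP 8.2 gives no baseline level, so the base case assumes a normal distribution with mean 17.7 (the earlier study's mean, Protocol 1.4.1) and SD 1.5, truncated to 12–20.

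**Step 1: reproduce SAP 8.2.** Marginal means are 3.85/7 = 0.55 and 23.00/7 = 3.286. Group variance = ((3.286 − 0.55)/2)² = 1.871, as stated. The mean off-diagonal correlation is 14.99/42 = 0.357, giving error terms √(9 × (1 + 6 × 0.357)) = 5.32 and √(9 × (1 − 0.357)) = 2.41; epsilon is 0.686. At 104 per group, power is >99.9% (group), 85.5% (time) and >99.9% (interaction), against the stated 99%, 85% and 99%. The inputs are read correctly.

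**Step 2: one visit by hand.** At baseline 17.7, the chance that a placebo subject reaches 22 is 1 − Φ((22 − 17.7 − 0.65)/3) = 1 − Φ(1.217) = 11% at Week 4, and 1 − Φ((22 − 17.7 − 0.35)/3) = 9% at Week 10. To stay untitrated, a completer must avoid both triggers at Weeks 4, 6, 8 and 10. Few placebo subjects can. The corresponding TRC101 chances of reaching 22 are 33% and 46%.

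**Step 3: simulation.** Bicarbonate = baseline + correlated normal change, 400,000 subjects per arm. The rules were applied at scheduled visits in Weeks 1–10: start at 2 packets, range 0–3, 14-day limit, values >30 counted as a decrease. Titration was given no effect. Ranges cover 48 scenarios: three baseline distributions; the SAP matrix or exchangeable correlation 0.333, 0.667 or 0.8; SD 2.5 or 3.0; baseline–change correlation 0 or −0.3.

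| Row | Placebo of 90 | TRC101 of 120 | TRC101 response |
|---|---|---|---|
| No titration | 1.1 (0.0–4.5) | 8.4 (4–23) | 80% (79–98) |
| Any up | 88.6 (84.4–90.0) | 104 (90–115) | 53% (46–60) |
| Any down | 1.4 (0.0–2.0) | 13.7 (1–18) | 83% (80–100) |

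Overall TRC101 response is 57%. The chance that the no-titration or any-down row has no placebo subject at all is about 50% (28% to >99%). The exact 95% CI for a placebo rate is 0–97.5% for 0/1 and 7–93% for 2/4.

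**Step 4: what the rows would show.** In the any-up row the between-arm difference is 41 points, against 44 overall (1–9 points lower across scenarios). In 20,000 simulated base-case trials, TRC101 response in no-titration minus any-up averaged 26 points (95% range −8 to 52; at least 20 points in 68%, under 10 in 14%). Any-down minus any-up averaged 30 points (6 to 50).

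**Step 5: early leavers.** They can stay untitrated and rarely enter the Week 12 responder comparison, but they do enter the MMRM row: "All scheduled blood bicarbonate values collected through the Week 12 visit will contribute to the analysis". With 5% leaving (the limit assumed in SAP 8.1), the placebo no-titration MMRM row holds 2.7 subjects if exits are spread over Weeks 1–10, or 5.5 if all occur by Week 2; about 1.0 has a Week 12 value. At correlation 0.8 the row holds 5.3 to 8.1, of whom 3.6 have one.

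**Step 6: overlap and definitions.** About 6.0 of 120 TRC101 subjects (0.0–9.5) are titrated both ways. Of these, 4.6 (0.0–8.0) are classed differently by 11.10 and 14.8.4: about 3.0 in the down group and 1.6 in the up group.

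**The case against.** The strongest objection is to the no-titration count. All 48 scenarios assume the algorithm is followed. Status reflects what was actually done, so an eligible subject who is not up-titrated stays in that row, and SAP 12.2 foresees investigational-product deviations and missed visits. The documents give no adherence rate. If 5%, 10% or 20% of subjects were never up-titrated (an assumption), the expected placebo no-titration count rises to 5.4, 9.8 or 18.6, and the TRC101 contrast with any-up falls to about 16, 12 or 7 points. This stands: the stated range for that row holds only under full adherence. The any-down row stays near 1 placebo subject, and a larger no-titration row would still be selected on outcome.

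The counts also need a baseline that SAP 8.2 does not give, and correlation 0.8 is not in the documents. The base case yields 57% and 13% response, a little above the planning rates of 50–55% and 10%. Fixing baseline at 17.7 gives 53% and 10.5%, with placebo rows of 0.65 and 0.90, which makes the sparsity worse. SAP 11.6 implies 82 + 108 + 27 = 217 randomised rather than 210, which changes little.

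SAP 13.3 will tabulate titrated and untitrated subjects by arm, so sparse rows will be visible, and Protocol 3.2.1 makes dose adjustment a stated interest. Both are fair context, but neither makes the comparison valid. It is also true that the SAP 16.1 wording refers to section 14.8, which would be kept; that is why the caveat belongs there as well.

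**Conclusion.** The concern holds, as a minor point. That titration status is set after randomisation by the endpoint variable, and then analysed between arms, follows from the text alone and needs no simulation.

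The sizes are model-based. They rest on the SAP 8.2 profiles, an assumed baseline distribution, full adherence and no titration effect. On those terms the no-titration and any-down rows hold about one placebo subject each, while any-up holds about 98% of placebo (88.6/90) and comes close to the overall result. A TRC101 contrast of some 26 to 30 points between rows is expected from selection alone, although a single trial need not show it. The no-titration figures are the least certain because of adherence.

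The analysis is exploratory and outside the testing sequence, so what is at risk is interpretation of a forest plot.

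**What to change.** 1. Delete titration status from the SAP 11.10 list, and so from the 14.6 between-arm analyses and the forest plots.
2. Keep the descriptive by-arm summary in SAP 14.8.4, with one definition of the status, and state how subjects titrated in both directions are shown.
3. Add one sentence there: the groups are defined by post-baseline bicarbonate, and differences between them do not estimate an effect of titration.
4. For the starting-dose question, refer to the randomised Week 4 comparison already reported by time point under 14.3.1 and 14.4.3, noting that some decreases or interruptions may come before it.

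The cost is one deleted bullet and two or three added sentences. No data collection, formal test, sample size or titration rule changes; only the between-arm rows for titration status are lost.
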